7.5.10.2 Analysis

Group 1

The change in prednisone or equivalent dose during TP1 will be analyzed descriptively, by visit and treatment groups as defined in Section 5.4.3.1. In addition, a figure by visit and treatment group will be produced, containing the change in prednisone or equivalent dose.

7.6.3 PGIC-F score at each post-baseline assessment

7.6.3.1 Variables

The PGIC-F is collected as defined in the visit and assessment schedule [see Appendix 12.1].

7.6.3.2 Analysis

The PGIC-F will be analyzed descriptively by visit and treatment group using the FAS with summary statistics as defined in Section 9.1 for categorical variables.

7.6.4 Change from baseline to each post-baseline assessment in SF-36v2™

SF-36v2™ data is collected using a paper CRF. Data is collected at Randomization, Month 6, Month 9 and Month 12 / premature EOT.

According to the questionnaire manual [Ware 2000], the following scores are considered:

- SF-36v2™ domain scores (0–100 scale): physical functioning, role physical, bodily pain, general health, vitality, social functioning, role emotional and mental health.
- SF-36v2™ domain scores norm-based: physical functioning, role physical, bodily pain, general health, vitality, social functioning, role emotional and mental health.
- SF-36v2™ PCS and MCS measures norm-based.
- SF-36v2™ reported health transition score.

7.6.4.1 Variables

The SF-36v2™ is a multi-purpose, short-form health survey with 36 questions. It yields an 8-scale profile of the functional health and well-being scores (i.e., physical functioning, role physical, bodily pain, general health, vitality, social functioning, role emotional and mental health) as well as psychometrically based physical and mental health summary measures and a preference-based health utility (health rated as ‘much better now than one year ago’, ‘somewhat better now than one year ago’, ‘about the same as one year ago’, ‘somewhat worse now than one year ago’, and ‘much worse now than one year ago’).

The following scores/measures are derived inhouse as described in the SF-36v2™ scoring manual using 1998 US population norms [Ware 2000] and detailed in Appendix 12.3 for the analysis:

- SF-36v2™ domain scores transformed to a 0–100 scale.
- SF-36v2™ domain scores norm-based (also known as T-scores).
- SF-36v2™ PCS and MCS measures norm-based (also known as T-scores).
- SF-36v2™ reported health transition score.

Missing items of incomplete questionnaires are imputed as described in Appendix 12.3. If, after applying imputation rules, the value at a given time point is missing (domain scores or component summary measures) then the value is considered missing.

Except for the reported health transition score (which is expressed as a subjective change in the question), the absolute change from baseline is defined as:

$$\text{Change of SF-36v2}^{\text{TM}} \text{ score} = \text{SF-36v2}^{\text{TM}} \text{ individual score at visit} - \text{SF-36v2}^{\text{TM}} \text{ individual score at baseline}$$

Baseline is defined as the last valid assessment prior to first study drug intake (by time and date).

7.6.4.2 Analysis

SF-36v2TM data will be analyzed using the FAS by visit and treatment group.

Summary statistics, by visit and treatment group, will be produced for all sub-scores and normalized sub-scores (physical functioning, role physical, bodily pain, general health, vitality, social functioning, role emotional and mental health, PCS and MCS). The health transition score will only be described at Month 12, and will be listed for all visits. Changes from baseline will be summarized for sub-scores and normalized sub-scores.

7.6.5 Change from baseline to each post-baseline assessment in the Lupus QoL questionnaire

The Lupus QoL questionnaire will be collected at Randomization, Month 6, Month 9 and Month 12/premature EOT. The Lupus QoL score is based on a questionnaire with 34 questions.

7.6.5.1 Variables

Calculation of Lupus QoL score

[figure not shown]
[REDACTED]

[REDACTED]

[REDACTED] 1.

The Lupus QoL consists of 34 items in eight domains. The number of items in each domain and the item numbers that refer to each domain are shown in Table 10.

Table 10 **Lupus QoL domains**

7.6.5.2 *Analysis*

The change in Lupus QoL score will be analyzed descriptively, by visit and treatment group, using the FAS. A figure of the change in Lupus QoL score over time will be produced using the FAS, by visit and treatment group.

7.6.6 **Change of mucocutaneous and musculoskeletal score from baseline (TP1)
up to Month 12**

7.6.6.1 *Variables*

The mucocutaneous score is defined as the weighted sum of each of the individual descriptors for the applicable organ class, i.e., mucosal ulcers, rash, and alopecia. The score is computed by summing up the standardized results for each descriptor.

The musculoskeletal score is defined as the weighted sum of each of the individual descriptors for the applicable organ class, i.e., arthritis and myositis. The score is computed by summing up the standardized result for each descriptor.

The mucocutaneous and musculoskeletal score is defined as the sum of the mucocutaneous and the musculoskeletal scores (computed above).

The absolute change from baseline (TP1) is computed as:

$$\text{Change in mSLEDAI-2K sub-score} = \text{mSLEDAI-2K sub-score at Visit X} - \text{mSLEDAI-2K sub-score at baseline (in TP1)}.$$

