3.2 Secondary objectives

The secondary objectives of the study are to evaluate the following over 6 months in adult subjects with moderate to severe SLE concurrently receiving background therapy:

- The safety and tolerability of cenerimod treatment.
- The effect of cenerimod treatment on QoL and fatigue using relevant PRO instruments.
- The effect of cenerimod treatment on SLE biomarkers.

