7.4.7.2 Analysis

An MMRM model will be used to analyze this endpoint including all monthly visits (similar to primary efficacy analysis in Section 7.2.5).

The following fixed effects will be included in the model: PGA baseline value, the two stratification factors (OCS and mSLEDAI-2K from IXRS), treatment group, month, treatment group by month interaction and PGA baseline value by month interaction.

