9 GENERAL STATISTICAL METHODOLOGY

9.1 General rules for data presentations

Unless otherwise specified, data will be summarized using appropriate descriptive statistics:

- For continuous variables: number of non-missing observations, mean, standard deviation, minimum, first quartile, median, third quartile and maximum.

Results will be displayed in the format of the eCRF for median, percentiles, minimum and maximum values. They will be displayed with one additional digit for the mean and the 95% CIs. The standard deviation will be displayed with one more digit than the mean.

- For dichotomous or categorical variables: number of non-missing observations, and frequency with percentage per category. Denominators for percentages are the number of subjects in the pertinent analysis set and treatment group, unless otherwise specified.

- For time-to-event variables: number of events, number at risk, number of censored observations and Kaplan-Meier estimates of the survival function.

In listings, subject number is presented as “SUBJID/SEX/AGE”.

A percentage change from baseline is defined as the absolute change from baseline divided by the baseline value (if the baseline value is > 0) and then multiplied by 100. In the event of baseline and post-baseline value both equal to 0, the ratio to baseline will be set to 1 (i.e., the percent change from baseline will be set to 0%). If baseline is equal to 0 and post-baseline value greater than 0 (infinite ratio) or if baseline greater than 0 and post-baseline equal to 0 ($\log[\text{ratio}] = \text{minus infinity}$), the percent change will be missing.

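### QoL is a secondary objective, but SF-36v2 and Lupus QoL get only by-arm descriptive summaries, with no planned dose-minus-placebo estimate or interval

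*SAP*

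**What the plan says.** SAP 3.2 lists as a secondary objective, over 6 months: "The effect of cenerimod treatment on QoL and fatigue using relevant PRO instruments".

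The analyses planned for the two QoL instruments are:

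- **SF-36v2 (7.6.4.2):** "Summary statistics, by visit and treatment group, will be produced for all sub-scores and normalized sub-scores", and "Changes from baseline will be summarized for sub-scores and normalized sub-scores".
- **Lupus QoL (7.6.5.2):** "The change in Lupus QoL score will be analyzed descriptively, by visit and treatment group, using the FAS", plus a figure of change over time.
- **Default content of a continuous summary (9.1):** "number of non-missing observations, mean, standard deviation, minimum, first quartile, median, third quartile and maximum". Confidence intervals appear there only in a rule on decimal places: "They will be displayed with one additional digit for the mean and the 95% CIs".

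On timing, 7.6.5 states: "The Lupus QoL questionnaire will be collected at Randomization, Month 6, Month 9 and Month 12/premature EOT". Section 7.6.4 gives the same times for SF-36v2. Within Treatment Period 1 each instrument therefore has a baseline value and one scheduled post-baseline value, at Month 6.

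**The concern.** In a placebo-controlled trial, the effect of a treatment is its difference from placebo. The plan sets out to evaluate that effect on QoL but stops at describing each arm. The difference, its precision and the adjustment for baseline are left to whoever reads the tables. If a QoL contrast is wanted once results are known, the scores, model and covariates will be chosen after the data have been seen. Both the baseline and the Month 6 scores are already collected, so nothing in the design prevents a prespecified estimate.

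**Working it through.** **1. Plan against objective.** The plan states no figure for this point, so the first check is of the text.

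| Needed to estimate the effect on QoL | SF-36v2 (7.6.4.2) | Lupus QoL (7.6.5.2) | General rules (9.1) |
|---|---|---|---|
| Change from baseline | Yes, summarized | Yes, summarized | n/a |
| SD of the change, by arm | Through 9.1 | Through 9.1 | Yes |
| Dose-minus-placebo difference | No | No | No |
| CI for that difference | No | No | No (decimal rule only) |
| Baseline score as covariate | No | No | No |

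**2. What a reader could derive.** From the by-arm n, mean and SD of the change:

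difference = mean(dose) − mean(placebo), with SE = √(SD²dose/n dose + SD²placebo/n placebo).

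This is a crude, unadjusted contrast, and no section plans to report it.

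**3. What baseline adjustment would change (illustration only).** Assume equal variance at baseline and Month 6, and correlation r between them. The documents give neither. In units of the score variance, the per-subject variance is 2(1 − r) for raw change and 1 − r² for ANCOVA. The ratio is

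(1 − r²) / [2(1 − r)] = (1 + r)/2.

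- r = 0.4: 0.84/1.20 = 0.70
- r = 0.5: 0.75/1.00 = 0.75
- r = 0.6: 0.64/0.80 = 0.80

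**4. Would the interval be informative?** SAP 2.1 gives about 325 subjects in five equal arms: 325/5 = 65 per arm. SAP 7.2.3 expects 6% missing at Month 6 for mSLEDAI-2K. Borrowing that rate for QoL (an assumption) gives 65 × 0.94 ≈ 61 per arm. The base 95% half-width for one dose against placebo is 1.96 × √(2/61) = 0.355 SD. It is multiplied by √[2(1 − r)] for raw change and by √(1 − r²) for ANCOVA.

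| Assumed r | Raw change, half-width (SD) | ANCOVA, half-width (SD) |
|---|---|---|
| 0.3 | 0.420 | 0.339 |
| 0.5 | 0.355 | 0.307 |
| 0.7 | 0.275 | 0.253 |

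An adjusted contrast would thus be known to within about 0.25 to 0.34 SD with the planned sample.

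**5. How many contrasts?** Eight Lupus QoL domains, eight SF-36v2 domains, PCS and MCS make 18 scores, counting the 0–100 and norm-based forms of an SF-36v2 domain once. With four doses, 18 × 4 = 72 contrasts. If no dose had any effect, 72 × 0.05 = 3.6 nominal 95% intervals would be expected to exclude zero. That argues for a short list of scores.

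**The case against.** The best defence is that QoL is secondary only as an objective. SAP 7.1 names two secondary endpoints, SRI-4 and BILAG-2004, and lists the PRO/QoL endpoints separately. The Type I error scheme in 7.1.1 covers the primary and secondary endpoints. Safety and biomarkers stand in the same list of secondary objectives and are also summarized by arm. Descriptive reporting is therefore consistent with the rest of this Phase 2b plan, and no section promises a QoL contrast. This stands: the plan neither contradicts itself nor breaches its testing strategy.

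Several stronger readings are tempting, but the documents do not support them:

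- **The tables carry no measure of uncertainty, or show raw means at the mercy of baseline imbalance.** SDs are tabulated, and change from baseline is derived per subject and summarized. What is missing is an interval for the difference and a baseline covariate.
- **The objective cannot be answered at all.** A crude difference can be built from the tables. The objective also covers fatigue, and sections 7.6.1 and 7.6.2 and any introduction to 7.6 are not in the available text.
- **QoL is treated worse than a lower-ranked endpoint.** For PGA change, 7.4.7.2 says: "An MMRM model will be used to analyze this endpoint including all monthly visits". But PGA is an other efficacy endpoint, and nothing shows that it ranks below QoL at endpoint level. The section shows only that a baseline-adjusted model is already specified in this SAP.
- **The variance ratio is a loss this trial suffers.** It compares two contrasts, neither of which the SAP plans.

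**Conclusion.** The point holds in a limited form. For SF-36v2 and Lupus QoL, the available text plans no between-arm estimate, no interval for a difference and no baseline covariate, although the effect on QoL over 6 months is a stated secondary objective. Primary and alpha-controlled secondary conclusions are untouched. This is an inexpensive improvement, not the repair of an error.

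Its size cannot be fixed from the documents. Given equal variances and r of 0.4 to 0.6, both assumed, ANCOVA would have 0.70 to 0.80 of the variance of a raw change-score contrast. The half-widths rest further on the borrowed 6% missing rate. The conclusion also assumes that no introduction to 7.6 supplies a general contrast. It says nothing about the fatigue instruments.

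**What to change.** Add the following to SAP 7.6.4.2 and 7.6.5.2:

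- **Model:** ANCOVA of change from baseline to Month 6 on the FAS, with treatment group, baseline score, and the OCS and mSLEDAI-2K strata from IXRS.
- **Output:** the LSM difference of each dose from placebo with a nominal 95% CI, labelled supportive and outside multiplicity control.
- **Scores:** a small set named in advance, for example SF-36v2 PCS and MCS and selected Lupus QoL domains. The remaining scores stay descriptive, which avoids 72 unadjusted contrasts.
- **Time point:** Month 6 only. A repeated-measures model with Months 9 and 12 is not needed for a 6-month objective, and it would have to deal with the re-randomization of the 4 mg arm at Month 6 (SAP 2.1).

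SAP 2.1 has one sponsor team unblinded at the Month-6 analysis. If that has already happened, the addition should be labelled as specified afterwards.

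The cost is a few extra tables, with a simpler model than the one in 7.4.7.2, and a set of nominal intervals that must not be read as tests. No extra subject, visit or alpha is needed.

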7.6.6.2 Analysis

The change in mucocutaneous and musculoskeletal score will be analyzed descriptively, by visit and treatment group, using the FAS.

7.7 Analysis of pharmacokinetic variables

See Section 6.10.

8 SAFETY VARIABLES AND ANALYSES

8.1 Overview of safety analyses including subgroup analyses

8.1.1 Safety endpoints

The following endpoints are defined according to protocol:

- Occurrence of TEAEs/SAEs, and AESIs [see protocol appendix 5, D-22.031].
- Occurrence of AEs leading to premature discontinuation of study treatment.
- Changes in 12-lead ECG variables (HR, PR, QRS, QT, QT corrected for HR on the basis of QTcB and QTcF), from baseline to each post-baseline assessment up to EOS (i.e., each post-dose time point on Day 1 / re-initiation and each post-dose analysis visit up to EOS) for each parameter.
- Occurrence of treatment-emergent 12-lead ECG notable abnormalities (e.g., HR, PR, QTc) [see protocol appendix 7, D-22.031].
- Occurrence of treatment-emergent 12-lead ECG abnormal findings.
- Change in supine SBP/DBP from baseline to each post-baseline assessment up to EOS (i.e., each post-dose time point on Day 1 / re-initiation and each post-dose analysis visit up to EOS).
- Change in FEV₁ and FVC from baseline to each post-baseline assessment up to EOS.
- Occurrence of treatment-emergent decrease of FEV₁ or FVC > 15% from baseline values at any post-baseline assessment.
- Change in laboratory parameters (hematology, blood chemistry, and urinalysis) from baseline to each post-baseline assessment up to EOS.

- Occurrence of treatment-emergent laboratory notable abnormalities [see protocol appendix 7, [D-22.031](#)].
- Change in body weight from baseline up to EOS.
- Change in left ventricular ejection fraction as assessed by Standard 2D/Doppler echocardiography from Screening to Month 6 in subjects randomized to ancillary echocardiography study.
- Occurrence of abnormalities as assessed by Standard 2D/Doppler echocardiography from Screening to Month 6 in subjects randomized to ancillary echocardiography study.

8.2 Adverse events

An AE is any event reported by the investigator on the Adverse Event eCRF page.

All AEs will be coded using MedDRA (most current version at time of database closure/snapshot).

AEs are classified according to the period of occurrence of the event. Periods are defined as:

- TEAEs
- AEs with onset during TP1
- AEs with onset during TP2

A more detailed description of rules for assigning AEs to the different periods is described below.

All AE tables will be summarized using the SAF. AE listings (all AEs, AEs leading to premature discontinuation of study treatment, SAEs, AESIs) will be produced using the SAF. A separate listing will be produced using the SCR to present AEs for non-treated subjects.

8.2.1 Variables

AEs are classified as ‘Treatment-emergent AEs’ if the start date of the AE is on or after the date of first study drug intake (by time and date) up to EOT + 180 days (inclusive).

AEs with onset during TP1 are defined in the interval:

[First study drug intake (by time and date); Month 6 visit or EOT
(if EOT date is on or before Month 6 visit date)]

AEs with onset during TP2 are defined in the interval:

[Month 6 visit + 1 day; EOT].

Any AE prior to start of treatment (by time and date) in TP1 and AEs 121 days or more after EOT are considered non-treatment-emergent AEs.

TEAEs on Day 1 are reported up to 24 hours after first study drug intake in TP1 and on or after the time of first study drug intake.

TEAEs on the day of re-initiation are defined in the same way, but for the day of the re-initiation.

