2 STUDY DESIGN AND FLOW

2.1 Study design

This is a Phase 2b, multicenter, randomized, double-blind, placebo-controlled, parallel group study to evaluate the efficacy, safety, and tolerability of cenerimod in subjects with moderate to severe SLE.

Approximately 325 adult subjects with SLE will be randomized in a 1:1:1:1:1 ratio to placebo, 0.5, 1, 2, or 4 mg once daily of cenerimod, in addition to background SLE therapy.

Once randomized, all subjects will enter a 6-month double-blind study treatment period defined as Treatment Period 1 (TP1).

Subjects randomized to, and still receiving, placebo, 0.5, 1, or 2 mg at Month 6 will continue their study treatment up to an additional maximum of 6 months in Treatment Period 2 (TP2), for a total maximum of 12 months.

Subjects randomized to the 4 mg arm will receive study treatment at this dose for a maximum of 6 months in TP1. Afterwards, subjects in this group, still receiving this dose

at Month 6, will be re-randomized in a 1:1 ratio to placebo or cenerimod 2 mg to enter TP2 and will continue for a total maximum of 12 months

Subjects who discontinue treatment in TP1 will continue study FU, performing study assessments, up to maximum duration of 12 months.

At EOT, subjects will enter a 6-month FU period (4-month before protocol Version 5).

Treatment allocation is stratified by dose of OCS at Randomization (two strata: < 7.5 mg/day or ≥ 7.5 mg/day prednisone or equivalent), and by disease activity at Screening (with two strata: mSLEDAI-2K < 10 or ≥ 10).

The study will be conducted at approximately 180 sites in 21 countries notably from the regions of Asia Pacific, Eastern Europe, Latin America, North America, and Western Europe.

No interim analysis is planned. There will be three study analyses: the Month-6 analysis, the Month-12 analysis and the final EOS analysis. Month-6 analysis will be performed when all randomized subjects have completed TP1 or discontinued the study. Month-12 analysis will be performed when all randomized subjects have completed TP2 or discontinued the study. Final EOS analysis will be performed when all randomized subjects have completed the post-treatment follow-up period or discontinued the study.

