5.6 Other derivations

The following conversion factors will be used to convert days into months or years: 1 month = 30.44 days, 1 year = 365.25 days. For time windows calculation, 1 month is expressed as 30 days.

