8.2.1.1 Missing values

Missing or partial dates for TEAEs are imputed as follows for the purpose of the treatment-emergent definition:

- AE start day missing: If the month and year is on or after the time and date of the first study drug intake month and year, and before or during the month and year of EOT + 180 days, consider the AE as treatment-emergent and impute the first day of the month, and if it is earlier than the first study drug intake, impute the first study drug intake date.
- AE start day and month missing: If the year is the same year as the year of first study drug intake or later, and if the year is prior to or in the same year as the year of EOT + 180 days, consider the AE as treatment-emergent and impute the date of first study drug intake.
- If the AE start date is completely missing then the AE is considered to be treatment-emergent (for TP1, but not for TP2).

If the time of an AE occurring on the day of first study drug intake is not recorded, the AE is considered to be treatment-emergent.

The same rule applies for AEs on the day of re-initiation.

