8.4.2 Variables

The absolute change and percent change from baseline in laboratory parameters (hematology, blood chemistry, and urinalysis) at each post-baseline analysis visit up to EOS is calculated as follows:

- Absolute change in laboratory parameters = Laboratory value at Visit X – Laboratory value at baseline (TP1)
- Percent change in laboratory parameters = (Laboratory value at Visit X – Laboratory value at baseline [TP1]) / Laboratory value at baseline (TP1) × 100

Absolute and percent changes are also derived based on the TP2 baseline.

Laboratory test abnormalities are defined as summarized in protocol appendix 7, for the following periods:

- During TP1: up to Month 6 for subjects who complete TP1 on treatment and up to EOT for subjects who discontinue study treatment during TP1.
- During TP2: up to EOT.
- Treatment-emergent (combining TP1 and TP2 data): up to EOT + 180 days.

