- (4) Echocardiography will be performed at Visit 1 (Screening) preferably within 30 days prior to Randomization for all subjects and at Visit 8 (Month 6) in approximately 175 subjects, as part of the ancillary study. In the event of premature study treatment discontinuation during TP1 (i.e., before Visit 8), echocardiography will be performed at pEOT visit and will not be required at Visit 8.
- (5) A chest X-ray that has been performed within 6 months prior to Screening can be used (in this case, there is no need to repeat the chest X-ray at Screening).
- (6) At each pre-dose assessment, SBP/DBP measurements will be performed twice in the supine position.
- (7) On Day 1 and at Re-initiation visit, SBP/DBP assessment and 12-lead ECG will be done pre-dose and hourly until 6 h post-dose; after 6 h, subjects may be discharged if they meet the discharge criteria, otherwise SBP/DBP assessments and 12-lead ECG will be performed hourly until discharge criteria are met. If discharge criteria are not met after 12 h, the subject must be permanently discontinued. At all other visits, only pre-dose SBP/DBP assessments and 12-lead ECG will be performed.

- (8) On Day 1 and at Re-initiation visit, 24-hour ECG Holter should start before dosing. The subject must return to the site on Day 2 (Visit 2a) / Re-initiation (Visit I2) for removal of the device after 24-hour recording.
- (9) On Day 1 and at Re-initiation visit, PK samples will be collected 6 hours after dosing. At Visits 3, 4, 5, and 8, PK samples will be collected pre-dose. At pEOT visit, in the event of premature treatment discontinuation during TP1 (i.e., before Visit 8) and at EOS visit, PK samples will be collected at any time during the visit and will not be required at Visit 8.
- (10) Hematology assessments, including coagulation tests will be performed at each visit until EOS, except FU2, FU3 and FU3a, and FU3b visits.
- (11) Serum pregnancy tests will be performed at Screening and EOS. Urine pregnancy tests will be performed at all other visits. To ensure compliance, the study personnel must remind WOCBP at each visit to use the methods of contraception defined for this study from the Screening visit until 6 months after taking the last dose of study treatment.
- (12) All AEs and SAEs occurring after signing the ICF and up to 6 months after study treatment discontinuation must be reported.

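### SAP 8.2.1 classes adverse events starting 121 to 180 days after end of treatment as both treatment-emergent and non-treatment-emergent

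*SAP*

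**What the plan says.** SAP 8.2.1 (Adverse events, Variables) contains two rules for the period after treatment. The opening sentence makes an event treatment-emergent if its start date "is on or after the date of first study drug intake (by time and date) up to EOT + 180 days (inclusive". Further down, after the intervals for onset in Treatment Periods 1 and 2, the section says that "AEs 121 days or more after EOT are considered non-treatment-emergent AEs". Both are current operative text, and nothing says which prevails.

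Elsewhere the SAP uses the longer bound:

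- Section 8.2.1.1, on partial start dates, takes an event as treatment-emergent if its month falls "before or during the month and year of EOT + 180 days".
- Section 8.4.2, on laboratory abnormalities, has "Treatment-emergent (combining TP1 and TP2 data): up to EOT + 180 days". The same bound appears in 8.5.2.3 (spirometry), 8.6.2.2 and 8.6.2.3 (ECG) and 8.7.1.3.1 (blood pressure).

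On follow-up, section 2.1 states: "At EOT, subjects will enter a 6-month FU period (4-month before protocol Version 5". The notes to the visit schedule in 12.1 require that adverse events occurring "up to 6 months after study treatment discontinuation must be reported".

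**The concern.** A treatment-emergent definition should divide events into two classes with no overlap and no gap. Here the two sentences overlap, so two programmers who each follow 8.2.1 can produce different counts, and independent quality control could not settle the difference from that section alone.

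The treatment-emergent tables in 8.2.2 are the only adverse event incidence tables that extend beyond treatment, because the tables by onset in each treatment period stop at EOT or earlier. If the 121-day sentence is coded as an exclusion, events on the disputed days leave the overview of treatment-emergent events and the tables by organ class, relatedness, intensity, seriousness, fatal outcome and special interest. The special-interest categories include infections and malignancies. A laboratory or ECG abnormality found on the same day would still count.

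The handling of dates would also become uneven. An event with a complete start date on day 150 could be excluded, while the same event with only month and year recorded would be treatment-emergent under 8.2.1.1.

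**Working it through.** No sample size, power or error rate is involved, and the plan gives no figure to reproduce. The check is a day-by-day comparison of the two rules, counting days after EOT.

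**Inputs**

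| Input | Value | Source |
|---|---|---|
| Last treatment-emergent day | 180, inclusive | SAP 8.2.1, opening sentence |
| First non-treatment-emergent day after EOT | 121 | SAP 8.2.1, later sentence |
| Bound for partial dates | 180 | SAP 8.2.1.1 |
| Bound for laboratory, spirometry, ECG, blood pressure | 180 | SAP 8.4.2, 8.5.2.3, 8.6.2.2, 8.6.2.3, 8.7.1.3.1 |
| Days in a month for time windows | 30 | SAP 5.6 |
| Follow-up after EOT | 6 months now, 4 months before protocol Version 5 | SAP 2.1 |

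**Overlap as written**

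- Days 1 to 120: treatment-emergent only.
- Days 121 to 180: both classes. Number of days = 180 − 121 + 1 = 60.
- Day 181 onward: non-treatment-emergent only.
- Share of the post-EOT window = 60 / 180 = 33%.

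**Where 121 may come from**

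Section 5.6 says: "For time windows calculation, 1 month is expressed as 30 days". Four months are then 4 × 30 = 120 days, and the next day is 121. Six months are 6 × 30 = 180 days. The 121-day cut-off therefore matches the former 4-month follow-up, and 180 days matches the current one. That the sentence was left behind when the window was extended is an inference; the SAP does not say so. The revision history for SAP version 5.0 does record that the treatment-emergent period was updated, for adverse events among others, because of evidence for a longer half-life.

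**Two ways to remove the overlap**

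| Change | Overlap (days) | Gap (days) | Agrees with the other sections? |
|---|---|---|---|
| Non-emergent from day 181 | 0 | 0 | Yes |
| Treatment-emergent to day 120 | 0 | 0 | No: 8.2.1.1, 8.4.2, 8.5.2.3, 8.6.2.2, 8.6.2.3 and 8.7.1.3.1 all use 180 |

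Both changes are logically clean, but only the first fits the rest of the SAP and the 6-month reporting period for adverse events.

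**The case against.** The strongest reply is that the intended rule is plain and the practical risk small. The sentence that defines the term gives 180 days, every parallel rule agrees, and none of the outputs listed in 8.2.2 summarizes non-treatment-emergent events. The stray sentence does harm only if someone uses it to override the definition. This is a fair account of intent and makes the correction easy. It does not remove the contradiction: the sentence is an explicit exclusion in the operative section, and it can be coded as such.

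Several limits on the consequences do stand:

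- **Deaths.** Section 8.3 summarizes deaths from their own eCRF page with no treatment-emergent window. Late deaths would leave the fatal and the combined death and serious-event treatment-emergent tables, but not that summary.
- **Listings.** The adverse event listings in 8.2 carry no 121-day limit, so late events would stay visible there.
- **Tables not affected.** The tables for the day of first intake, the day of re-initiation and onset in each treatment period cannot change.
- **The contrast with laboratory and ECG data.** For subjects who complete treatment, no laboratory test is scheduled at the second to fifth follow-up contacts, and the only follow-up ECG is at the end-of-study visit. On the disputed days the contrast arises mainly at that visit, at unscheduled tests, or in subjects who stopped early and stay on the visit schedule.
- **The meaning of 33%.** It is a share of post-EOT days, not of events or subjects. For a subject treated for 360 days, the whole treatment-emergent window is 360 + 180 = 540 days, and the disputed part is 60 / 540 = 11%. Subjects whose follow-up ended under the 4-month schedule may have no observation there at all.

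No efficacy hypothesis, error rate or estimand depends on this point.

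**Conclusion.** The concern holds. Section 8.2.1 is wrong as written: 60 days after EOT, one third of the post-treatment part of the window, carry two opposite classifications with no rule to choose between them. The conclusion rests only on the two sentences in that section and needs no outside figure. That 180 days is the intended bound is inferred from its use in every other section that defines a treatment-emergent period and from the 6-month reporting of adverse events.

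The number of events at stake is unknown. It depends on how many subjects were followed past day 120 and on what was reported after that day, and the documents give neither. The exposed outputs are the treatment-emergent tables that extend past EOT. Because these carry the main safety summary for follow-up, the definition should be corrected before they are programmed.

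**What to change.** In SAP 8.2.1, change the start of the post-treatment non-emergent class from 121 days or more after EOT to more than 180 days after EOT. The class is then the exact complement of the treatment-emergent class, with no overlapping day and no gap, and it agrees with 8.2.1.1, 8.4.2, 8.5.2.3, 8.6.2.2, 8.6.2.3 and 8.7.1.3.1. Any programming specification that carries the 121-day limit should be changed to match.

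The cost is one phrase in the SAP. Data collection and the visit schedule do not change, because adverse events are already reported for 6 months after treatment stops.
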